Because frequent use during the day (six times; each 2 hours) and high viscosity of gum arabic solution, which lead to withdrawn some patients after were enrolled in this study. Researcher was tried to solve this problem at two sides; firstly, by increasing the quantity of purified water as solvent for Gum Arabic to 250 milliliters instead of 100 milliliters to reduce viscosity of solution. On the other hand, patient was informed to use this quantity of solution twice daily; half at 9 morning and the remaining half at 9 evening to decrease frequent uses.

Oral mucositis assessment:

Based on a combination of subjective, objective and functional outcomes, using World Health Organization Oral Toxicity Scale (WHO Score): subjective – soreness as described by the patient, objective – presence of erythema and ulcerations, and functional – ability to eat solids, liquids or nothing by mouth

Assessment gum Arabic effect

For each participant data of oral mucositis will be start after getting ethical committee permission & permission from Radiation and Isotopes Center of Khartoum (RICK) authority. Informed consent also will be taken from study participants.

Data will gather via data collection sheet which composed of two sections; that will fill through six weeks of patient follow up. The first part for assessment patient regarding oral mucositis after chemotherapy by weekly telephone call for patient based on ready-scheduled appointments. The second part contain a basic information and characteristics of patient, which will record by researcher during the first day at first cycle of chemotherapy. In addition, there is meeting with patients by researcher in chemotherapy rooms when the participant return to the next cycle of chemotherapy either weekly, bi-weekly or every three weeks, according to treatment regimen.

When the researcher is contacted with the patient either by telephone call or when meeting participant in the hospital during the next chemotherapy cycle; there will be specific questions directed by the researcher to be answered by the patient regarding oral mucositis. Those questions will be summarized as follow: 1. Does the oral mucositis was occurred during this week? 2. If Yes. Is there was soreness, erythema, ulcers in mouth of participant? 3. The day that oral mucositis was started and eliminated? 4. If the patient belong to study group; Is Gum Arabic still used regularly? Six weeks for each participant from starting therapy.

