Cessation of trial therapy

No stop for recruiting the participants to study group until the planned number was completed, but there was a period of three weeks the new recruitment was suspended to separate study group from control group in try to reduce the bias (reduce the confounding) between the two groups and give a chance to follow up the study group patients. By August 2016 we stopped participants recruitment and follow up; since the sample size proposed and follow up planned was completed.

Statistical analysis

The collected data were arranged, coded, tabulated, and introduced to a personal computer using Statistical Package for Social Science (IBM SPSS Statistics 20.lnk). P. values equal or less than 0.05 was considered significant. The data of 332 patients who completed this study were documented and reviewed to give a qualitative analysis of the frequencies. The descriptions were based on the data that documented from personal file of patient in designed sheet prepared by the researcher. Data were presented and suitable analysis was done according to the type of data obtained for each parameter. All numeric variables were expressed at 95% confidence intervals. Student t-test was used to assess the statistical significance of the difference between means of the two groups.

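### If mucositis duration is compared by the t-test, episodes still open at six weeks are cut off or dropped, which understates duration and can favour a later-onset group

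*Combined protocol and SAP*

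**What the plan says.** Under Assessment gum Arabic effect, the data sheet is described as one "that will fill through six weeks of patient follow up". Patients are contacted "by weekly telephone call for patient based on ready-scheduled appointments" and are also seen when they return for chemotherapy. One of the four listed questions asks for "The day that oral mucositis was started and eliminated". The period is given as "Six weeks for each participant from starting therapy", and no contact after that is described. Under Cessation of trial therapy the document says "By August 2016 we stopped participants recruitment and follow up", again with no mention of following an episode to its resolution.

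Under Statistical analysis the one named test is given as: "Student t-test was used to assess the statistical significance of the difference between means of the two groups". No variable is attached to it. The section also says that "suitable analysis was done according to the type of data obtained for each parameter", without naming the analyses. Nowhere is there a rule for an episode unresolved at last contact, or a time-to-event method.

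**The concern.** An episode that is present at day 42 has a start day but no end day. Anyone who computes a mean duration from these data has two simple choices: treat day 42 as the end, or leave the episode out. The first shortens that episode. The second removes long episodes selectively. The t-test then takes the remaining values as complete.

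The later an episode starts, the more likely it is to be open at day 42, so the shortening is not shared equally if the groups differ in onset. The stated objective is prevention, and an agent that only delayed onset could then appear to shorten episodes as well. At stake is whether an apparent difference in mean duration can be read as an effect on duration.

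**Working it through.** **Inputs from the documents.** Follow-up is 6 x 7 = 42 days from the start of therapy. Contact is weekly, plus chemotherapy visits that may be weekly, two-weekly or three-weekly. The stated threshold is "P. values equal or less than 0.05 was considered significant", taken here as two-sided. The analysed number is 332 completers, with no split between groups. The documents give no onset days, durations, incidence, power or effect size, so there is no figure of the plan's own to reproduce. Everything below on onset and duration is assumed.

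**Definitions.** Let T be the day of onset and D the true duration. An episode is open if T + D > 42. Cutting off records min(D, 42 - T). Dropping keeps D only where T + D <= 42. Both give a mean at or below the true mean.

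**Share of episodes open at day 42**

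| Assumed onset | Assumed duration | Mean 7 d | Mean 10 d | Mean 14 d |
|---|---|---|---|---|
| 5-14 days after the first cycle only | gamma, shape 4 | about 0% | about 0% | about 2% |
| 5-14 days after a cycle at day 0 or day 21, equal odds | gamma, shape 4 | 7% | 18% | 30% |
| Uniform over 42 days | exponential | 17% | 23% | 32% |

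The first two rows are simulated. The third has a closed form, with m the true mean: share = (m/42) x (1 - exp(-42/m)). For m = 10 this is 0.2381 x (1 - 0.0150) = 0.2345.

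**Understatement of the mean.** For uniform onset the cut-off mean is m x (1 - share), which gives 5.8, 7.7 and 9.6 days for true means of 7, 10 and 14. Dropping open episodes gives 5.6, 7.1 and 8.5 (simulated). At the other extreme, with onset centred on day 10 (normal, SD 4 days) and a true mean of 10 days (gamma), 0.3% of episodes are open and the means are 9.99 (cut) and 9.95 (dropped).

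**False difference between groups, equal true mean of 10 days.** Suppose onset is uniform from day 0 to 42 in one group, and from day s to 42 in the other. With W = 42 - s, share = (10/W) x (1 - exp(-W/10)).

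- s = 7: share = 0.2771, cut-off mean = 7.23, difference = 7.65 - 7.23 = about 0.43 day. Dropping gives about 0.55 day.
- s = 14: share = 0.3354, cut-off mean = 6.65, difference = 7.65 - 6.65 = 1.0 day. Dropping gives about 1.3 days.

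**False rejection by the t-test, equal true durations.** Simulation with gamma durations (shape 4), onset normal with SD 4 days, 83 episodes per group and 2,000 replicates:

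| True mean | Mean onset day, two groups | Cut at day 42 | Dropped |
|---|---|---|---|
| 10 d | 10 v 13 | 4.9% | 4.8% |
| 7 d | 10 v 17 | 4.7% | 4.7% |
| 10 d | 10 v 24 | 9.0% | 26.2% |
| 10 d | 20 v 27 | 19.6% | 36.7% |
| 10 d | 25 v 30 | 52.2% | 44.0% |
| 14 d | 10 v 24 | 40.2% | 78.9% |

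Wherever rejection was clearly inflated, almost all rejections favoured the later-onset group. With every episode followed to its end, rejection was 4.0% to 6.1% across all scenarios run. The inflation therefore comes from the handling of open episodes, not from the t-test as such.

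**The case against.** The strongest objection is that the documents do not specify this analysis. The objective is prevention, duration is never listed as an outcome, and the t-test is tied to no variable. It could have been meant for baseline or other numeric data, and the wording about suitable analysis by data type leaves room for another method. This stands, and it is why the point is conditional. The inference is still reasonable. Of the four listed mucositis questions, only the one on start and end days yields a numeric value from which a mean can be taken, and no other named test is available for it.

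The second objection is that uniform onset guarantees many late episodes and is only one choice. This also stands. If onset follows only the first cycle, almost no episodes are open. Against that, the plan describes repeated cycles within the six weeks, so later onset is plausible.

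A reader might infer that any group with later onset gains an advantage. That is too strong: a three-day difference early in follow-up produced no visible inflation. A reader might also infer that the trial did compare durations by t-test, or that a finding of shorter mucositis would be false. The documents support neither, since they report no such comparison and give no count of open episodes.

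**Conclusion.** The concern holds in conditional form. Start and end days are collected within a closed 42-day window, no rule covers an unresolved episode, and the only named test has no means of handling one. If duration is compared by that test, it is understated, and the comparison can favour a group with later onset.

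The direction is firm when true durations are equal. The size is unknown: it may be negligible (early onset, short episodes) or large enough to distort the test severely (late onset or long episodes). The range of 0% to 32% open rests wholly on assumed onset patterns and assumed true means of 7 to 14 days. The number of open episodes in each group would settle which case applies.

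**What to change.** 1. State whether episode duration is analysed. If it is, use Kaplan-Meier with open episodes censored at day 42 or at last contact, instead of a t-test. Because the onset day fixes the censoring time, this assumes that an episode's length is unrelated to when it started, and the plan should say so.
2. Analyse time to first mucositis by Kaplan-Meier and log-rank, with the same censoring. This is where a delay in onset should be shown.
3. Report the number of episodes open at last contact in each group.
4. Days with mucositis in days 1-42, scored 0 for patients with none, may be reported for every patient. It must be labelled as total burden, because it reflects incidence, onset and duration together. With exponential durations of mean 10 days in both groups, moving a uniform onset later by 7 or 14 days (onset after day 42 scores 0) lowers it from 7.65 to about 6.0 or 4.4 days. It is not evidence of shorter episodes.

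The cost is a modest re-analysis. Follow-up ended by August 2016, the document is dated 15/11/2017, and the analysis is written in the past tense, so this is more than a change of wording. The onset, end and contact days are already in the plan's data collection, and the methods are standard in SPSS.

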Using Gum Arabic for Cancer Patients to Protect From Oral Mucositis Caused by Chemotherapy: An Experimental Study

NCT ID not yet assigned

15/11/2017

Study protocol

Background

Investigate agents which can be used to prevent or treat chemotherapy-induced oral mucositis is a primary concern for clinicians and researchers. The synthesis pharmacological drugs are costly and associated with much side effects resulting in patient non-compliance. So, there is a need to find alternative therapies especially from natural sources as these are cost effective and have no or minimal side effects. In this regard, Gum Arabic is very convenient since this polymer is readily available on nature and does not require any further complex method of purification. Also it is a safe material for biological applications.

Objective of study

The purpose of this research was to investigate the effect of Gum Arabic to prevent chemotherapy-induced oral mucositis in cancer patients.

Inclusion criteria

Patients whom well diagnosed with cancer in any stage were eligible for enrolment if chemotherapy is a part of the treatment plan.

Exclusion criteria

Patients will be excluded if recently received chemotherapy or radiotherapy, presence of oral mucositis or periodontitis, or there is evidence of any systemic diseases.

Dose, preparation and administration of gum arabic

The daily dose of Gum Arabic will be divided in 30 grams sachet, the content of sachet will dissolve once in 100 ml purified water to form solution, and consuming

in six divided doses. Patient will provide by measuring cap to using 20-ml every two hours as mouthwash for a minute then swallow.

The total number of sachets are 42 for a period of six weeks; each patient will give 21 sachet of Gum Arabic at the first day of chemotherapy treatment to be used during the next three weeks of the treatment period, then the remain quantity (21 sachets) will provide for the next three weeks.

Modification on the preparation and administration

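### No allocation method is stated, the groups appear to have been recruited one after the other, the only named comparison is an unadjusted t-test, and a three-week recruitment pause cannot reduce confounding

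*Combined protocol and SAP*

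**What the plan says.** All references are to the combined protocol and SAP.

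- **Recruitment (Cessation of trial therapy).** "No stop for recruiting the participants to study group until the planned number was completed". The same sentence continues that "there was a period of three weeks the new recruitment was suspended to separate study group from control group". The reason given is "in try to reduce the bias (reduce the confounding) between the two groups", together with time to follow up study-group patients. The section closes with "By August 2016 we stopped participants recruitment and follow up".
- **Allocation.** Nothing is said about randomisation, concealment, matching, stratification or group sizes. The only design label is the title's description of the study as experimental.
- **Analysis (Statistical analysis).** "Student t-test was used to assess the statistical significance of the difference between means of the two groups". A general sentence adds that "suitable analysis was done according to the type of data obtained for each parameter". No covariate or adjusted model is named. The analysis covers 332 patients who completed the study, and the split by group is not given.
- **Eligibility.** "Patients whom well diagnosed with cancer in any stage were eligible for enrolment if chemotherapy is a part of the treatment plan". On the other side, "Patients will be excluded if recently received chemotherapy or radiotherapy", and existing mucositis or periodontitis and systemic disease are also exclusions.
- **Data available (Assessment gum Arabic effect).** Patient characteristics are recorded on the first day of the first cycle. Cycle intervals differ by regimen, from weekly to three-weekly. Each participant is followed for six weeks.

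**The concern.** The stated objective is causal: whether gum arabic prevents chemotherapy-induced oral mucositis. An unadjusted comparison answers that only if the two groups would have had similar mucositis risk without it. Random allocation would give that assurance, but none is described.

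If the groups were filled one after the other, group membership coincides with calendar period. Any drift in regimens, referral pattern, supportive care or the way mucositis was asked about is then part of the group difference. Even without drift, nothing in the plan ensures a similar mix of stage, tumour site and regimen.

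The plan treats the pause as the safeguard. A pause may limit contact or product sharing between groups, and it frees time for follow-up. Those are contamination and logistics, which are separate matters from confounding. A reader who accepts the statement would credit the comparison with a protection it lacks. The p-value and 95% confidence interval would then describe sampling error around a difference that may itself be confounded.

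**Working it through.** **1. What the text supports.** The plan gives no power, effect size or event rate, so it has no figure of its own to reproduce. The recruitment sentence has three elements in order: uninterrupted recruitment to the study group up to its planned number, a three-week suspension separating the groups, and time to follow the study group. Study group first and controls second is the natural reading, though it is not stated outright.

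**2. What the pause can do.** Follow-up is 6 weeks and the pause is 3 weeks. If the pause began at the last study-group enrolment, that patient still had 6 − 3 = 3 weeks to run when controls started, so even the follow-up periods may not be fully separated. The length of the pause does not enter any of the calculations below. Only case mix, or adjustment for it, does.

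**3. Illustration of case-mix imbalance.** From the documents: total N = 332 and significance at p≤0.05. Assumed, because the documents do not give them: a two-sided test, a 1:1 split (166 per group), one binary prognostic factor (higher-risk or other regimen), mucositis risks of 60% and 30%, and the higher-risk share in each group.

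Crude risk = share × 0.60 + (1 − share) × 0.30

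- share 0.40: 0.24 + 0.18 = 0.420
- share 0.55: 0.33 + 0.135 = 0.465
- share 0.60: 0.36 + 0.12 = 0.480

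The rejection rate sums the binomial probabilities of every pair of event counts for which the pooled two-sided Student t-test on 0/1 outcomes gives p≤0.05. The treatment has no effect in this table.

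| Higher-risk share, study v control | Crude risks | Difference | Rejects, 166 v 166 |
|---|---|---|---|
| 40% v 40% | 0.420 v 0.420 | 0 | 5.2% |
| 47.5% v 52.5% | 0.4425 v 0.4575 | 1.5 points | 6.2% |
| 45% v 55% | 0.435 v 0.465 | 3.0 points | 9.0% |
| 40% v 55% | 0.420 v 0.465 | 4.5 points | 13.6% |
| 40% v 60% | 0.420 v 0.480 | 6.0 points | 20.4% |

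A normal approximation gives 13.1% and 19.6% for the last two rows.

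**4. Sensitivity of the last two rows.**

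- Split 221 v 111: 12.3% and 18.2%.
- Risks 50%/30%, 166 per group: 8.6% and 11.5%.
- Risks 70%/20%, 166 per group: 28.8% and 46.1%.

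**5. Opposite direction.** Take a true risk ratio of 0.75, with the study group carrying more higher-risk patients (60% v 40%). The crude risks are 0.75 × 0.480 = 0.360 v 0.420, so the crude ratio is 0.360/0.420 = 0.86 and power is 20.0%. With shares of 50% in both groups the risks are 0.75 × 0.450 = 0.3375 v 0.450, and power is 55.5%.

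**6. Adjustment.** In 3,000 simulated trials per setting, a modified Poisson model with robust variance, adjusted for regimen risk, gave false-positive rates of 5.3% (40% v 55%) and 4.6% (40% v 60%). Under the true ratio of 0.75 with shares of 60% v 40%, power was 58.6% and the mean estimated ratio 0.75.

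**The case against.** The sequence is inferred. No dates or group order are given, and the English is loose. If patients were in fact allocated concurrently, the calendar argument falls away. If recruitment was sequential, the ordering creates the alignment with calendar period, and the pause only adds three weeks to it. The length of recruitment is unknown, so a period effect might be small. All of this stands, and it is why dates and allocation must be stated first. It does not rescue the claim about confounding, which fails under either reading.

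The wording on the pause states an intention, names bias before confounding, and adds a logistical purpose. A misused term alone could be fixed by rewording. That is fair, but here the phrase stands where a design or analysis safeguard should be.

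The plan ties the t-test to means and leaves room for other tests by type of data. It does not say that yes/no mucositis was t-tested. This is correct, but a two-proportion comparison gives almost the same rates, and no alternative in the text includes adjustment.

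No input to the illustration on risk or imbalance comes from the documents, and small imbalances inflate the error rate little. The near-complete recovery under adjustment arises because the model adjusts for the only confounder simulated, measured without error. Both points stand. The figures show the mechanism and do not estimate bias in this study, and real adjustment would achieve less. The exclusion criteria also remove some imbalance, but they leave stage, tumour site and regimen open.

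**Conclusion.** The concern holds. No allocation method is described, the only named between-group comparison is unadjusted, and a recruitment pause cannot reduce confounding. An unqualified prevention claim is therefore not supported by the plan as written.

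The size and direction of any bias are unknown. On the assumed inputs, false-positive rates run from about 6% for a 5-point imbalance to about 20% for a 20-point imbalance, and up to 46% if regimen risks differ more sharply (70%/20%). An imbalance the other way can cut power from 56% to 20%. The conclusion rests on the text and would stand without these figures.

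The calendar-period part depends on recruitment having been sequential. If the groups did not overlap in time, no analysis can separate period from treatment. This needs correction before results are interpreted. Confidence is medium because the sequence is inferred.

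**What to change.** 1. State how patients came to be in each group, the first and last recruitment dates for each group, and the group sizes.
2. Remove the statement that the pause reduced confounding. Describe it as a measure for follow-up workload and, if intended, for limiting contact between groups.
3. Present baseline characteristics by group.
4. Add a regression with group plus baseline factors: for example, modified Poisson for any oral mucositis and Cox for time to onset. Candidate covariates are regimen, cycle interval, tumour site, stage, age and sex, where recorded. A stratified or standardised analysis would also serve.
5. Label the adjusted analysis post hoc, since recruitment and follow-up had ended by August 2016, and show the unadjusted result beside it.
6. State that adjustment covers measured factors only and cannot remove calendar-period effects. If the dates confirm sequential recruitment, word the conclusion as an adjusted association from non-concurrent groups.

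**Cost.** No new patients or visits: one or two models, a baseline table and wording changes. The documents do not list the day-one variables, so some covariates may be incomplete or need extraction from patient files. The conclusion becomes more cautious.

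### The only analysis set described is the 332 completers, although gum arabic led some enrolled patients to withdraw, so the comparison is at risk of attrition bias of unknown size and direction

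*Combined protocol and SAP*

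**What the plan says.** The Statistical analysis section names a single set: "The data of 332 patients who completed this study were documented and reviewed to give a qualitative analysis of the frequencies". The sentence on the t-test names no set of its own. No all-enrolled set, missing-data rule or sensitivity analysis appears anywhere.

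The section Modification on the preparation and administration reports that six uses a day and the solution's viscosity were a problem "which lead to withdrawn some patients after were enrolled in this study". The preparation and schedule were then changed during the study.

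Under Assessment gum Arabic effect, each participant is followed for six weeks, "by weekly telephone call for patient based on ready-scheduled appointments", with further meetings at chemotherapy visits. The questions cover occurrence, dates ("The day that oral mucositis was started and eliminated") and, for the study group, adherence: "Is Gum Arabic still used regularly".

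Cessation of trial therapy says that study-group recruitment continued until the planned number was reached and that "there was a period of three weeks the new recruitment was suspended to separate study group from control group". It ends: "By August 2016 we stopped participants recruitment and follow up; since the sample size proposed and follow up planned was completed". The proposed sample size itself is not stated.

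**The concern.** Control patients did not take gum arabic, so they could not withdraw because of its viscosity or frequency of use. Loss of this kind falls on one group only. If those patients are left out, the remaining study-group patients are those who tolerated the product, compared with controls who passed no such filter. A difference in mucositis could then come partly from selection.

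The bias favours gum arabic only if withdrawers had a higher mucositis risk than completers; if their risk was lower, it works against gum arabic. The reasons given for withdrawal are about convenience and texture, not mouth symptoms, so they do not settle the direction. The change of preparation may also have reduced later withdrawals. If few patients left, or their risk was like that of the others, the effect is small. A reader cannot tell which case applies.

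**Working it through.** **What can be reproduced.** The 332 is a count of completers, not a derived sample size. No effect size, event rate, power, allocation ratio, dropout rate or number enrolled is given, so neither the 332 nor the number missing can be worked out.

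**Assumptions for the illustration (none is in the documents).** 166 completers per group (332/2); a yes/no mucositis outcome over six weeks; 40% risk in controls; withdrawn share *w* of 5%, 10% or 20%, in the study group only unless stated. The test is the two-sided pooled two-proportion test at 0.05, with z = (p1 − p2)/√[p(1 − p)(1/n1 + 1/n2)], where p is the pooled risk.

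**1. No true effect.** If all enrolled study-group patients have risk 0.40 and withdrawers have risk *r*, completer risk = (0.40 − w·r)/(1 − w). For example, w = 0.20 and r = 0.80 give (0.40 − 0.16)/0.80 = 0.300. Each cell shows completer risk, then the rejection rate against a control risk of 0.40:

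| w | r = 0.20 | r = 0.40 | r = 0.60 | r = 0.80 |
|---|---|---|---|---|
| 5% | .411; 5.4% | .400; 5.0% | .389; 5.4% | .379; 6.8% |
| 10% | .422; 7.0% | .400; 5.0% | .378; 7.0% | .356; 13.3% |
| 20% | .450; 15.1% | .400; 5.0% | .350; 15.6% | .300; 48.0% |

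The rates count both directions. In the r = 0.20 column the excess is false harm; at r = 0.60 and 0.80 it is false benefit. With r = 0.50, ten points above base, the rates are only 5.1%, 5.5% and 7.5%. A 222/110 split either way gives 6.5% to 6.7%, 12.0% to 12.6% and 42.7% to 44.5% at r = 0.80, so the equal split is not critical.

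**2. Bounds on an assumed completer result of 25% v 40%.** The difference is 15.0 points (95% CI 5.1 to 24.9, p = 0.0035). Study-group enrolment is 166/(1 − w). Worst-case risk is (1 − w)·0.25 + w; best-case risk is (1 − w)·0.25.

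| w | Worst case v 40% | p | Best case | Best-case difference |
|---|---|---|---|---|
| 5% | 28.75% | 0.029 | 23.75% | 16.25 points |
| 10% | 32.5% | 0.144 | 22.5% | 17.5 points |
| 20% | 40.0% | 1.0 | 20.0% | 20.0 points |

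If controls withdrew at the same rate and all of them are counted as free of mucositis, the worst case is 28.75% v 38.0% (p = 0.067) at 5% and 32.5% v 36.0% (p = 0.479) at 10%.

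**3. The same in whole patients.** Take 42/166 v 66/166 (p = 0.005) and add *k* study-group withdrawers:

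- All with mucositis: k = 10 gives 52/176, p = 0.047; k = 11 gives 53/177, p = 0.056, where 11/177 = 6.2% withdrawn.
- At the assumed control risk of 40%: k = 9 adds 3.6 expected cases, p = 0.007; k = 18 adds 7.2, p = 0.010.

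A few withdrawals could therefore remove significance at the extreme bound, but change little if withdrawers resembled controls.

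**The case against.** The strongest reply is that exclusion of the withdrawers is not established. Weekly calls did not depend on taking the product, and asking whether gum arabic was still in use implies that some patients would be followed after stopping. If completion means six weeks of follow-up, patients who stopped only the product may already be among the 332. This stands, and it is why the point is a risk of bias and not a demonstrated one. It does not remove the problem, because the text does not say whether these patients left the product or the follow-up.

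A second reply is that every rate in the illustration is assumed and the extremes can alarm. That also stands: no passage supports withdrawers at twice the base risk, and the moderate cases are mild. The switch between 10 and 11 patients also depends on the test; Fisher's exact test already gives p = 0.053 at 10. The figures apply to a yes/no outcome and do not carry over to a t-test on grade or duration.

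A third is that the completer sentence introduces frequencies, not the t-test. But occurrence of mucositis is itself a frequency, and no other set is offered for the t-test.

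Finally, groups apparently recruited in separate periods, with no randomisation described, raise a confounding problem that this point does not address. That is correct, and it is a separate matter. Recruiting until the planned number was reached is also compatible with replacing withdrawn patients, though replacement is not stated. If it happened, reaching the target would hide the losses.

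**Conclusion.** The concern holds and should be fixed. The plan describes only a completer set, reports withdrawal from a cause confined to one group, and omits the counts and the definition needed to judge the consequence. The size and direction of any bias cannot be determined from the documents. Under the stated assumptions the effect ranges from negligible (5% withdrawn, or withdrawers with risk near that of completers) to serious (20% withdrawn at twice the base risk). Confidence is medium, because the withdrawn patients may be among the 332 and because the illustration rests on assumed risks and group sizes.

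**What to change.** - Define completion. Report enrolled, withdrawn and completed patients by group, with the reason and timing of each withdrawal, whether it was from the product or from follow-up, and whether it came before or after the preparation changed.
- Make the main comparison all enrolled patients in the group they entered, regardless of continued use. The weekly records and onset dates allow time to first mucositis, censored at last contact, with the Kaplan-Meier six-week risk by group and the difference with its 95% CI. State that this assumes withdrawal is unrelated to later risk. A simpler all-enrolled risk comparison would also deal with completer selection.
- Add best-case and worst-case bounds for withdrawn patients in both groups, including any with no contact after baseline.
- Keep the 332-completer analysis as secondary.
- Label the reanalysis post hoc, since follow-up had ended by August 2016. Say that it addresses attrition only, and that an all-enrolled analysis spans both preparations.
- If withdrawers' records were not kept, report counts and bounds and limit the conclusion to patients who completed follow-up.

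The cost is a little extra analysis and one table. The estimate may become less favourable to gum arabic, or the conclusion narrower. The change does not make the two groups comparable.
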